2.1.2 Effectiveness Results

Procedural success, defined as the successful creation of an endoAVF with blood flow confirmed intraoperatively by fistulography or postoperative duplex ultrasonography, was achieved in 96.7% (88/91) of the population. Using Kaplan-Meier (KM) point estimates at month 6, the cannulation success rate was $84.9\% \pm 5.3\%$ for participants in the HD subset. The mean time to cannulation was 2.0 ± 1.6 months.

Primary patency and cumulative patency were determined using the KM point estimates at month 6. Primary patency was $72.4\% \pm 5.2\%$ and cumulative patency was $77.3\% \pm 5.0\%$. Functional patency was 100% through 6 months in the population who used their endoAVF for HD.

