4.1.2 Primary Effectiveness Endpoint

Interventions Post Creation to Facilitate AVF Use and / or Maintain AVF Use (Facilitation and / or Maintenance Interventions) through the Timepoint of the 6-Month Follow-Up of the Last Active Treated Participant

The primary effectiveness endpoint is the number of interventions post creation to facilitate and / or maintain AVF use (facilitation interventions and / or maintenance interventions as defined in Section 4.4). The procedures that will be evaluated as part of this endpoint are indicated in Table 1 in Section 4.4 and exclude adjunctive and second stage procedures.

The number of facilitation and / or maintenance interventions per PY will be compared to a PG that is composed of the combined targets for interventions to facilitate and maintain AVF use recommended by the 2019 update of the KDOQI Clinical Practice Guideline for Vascular Access.⁸ This endpoint will be evaluated including all data collected for all participants up until the timepoint of the 6-month follow-up of the last active treated participant (i.e. including any and all data exceeding the 6-month follow-up visit up to this timepoint).

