4.4 Applicable Endpoint Definitions

Access Abandonment (permanent abandonment) is defined as the point at which the access can no longer be used for one or two needle prescribed HD as it may be unable to provide adequate flows and / or is deemed unsafe for the participant, and the associated problem cannot be corrected by any further intervention, including medical, surgical, or endovascular interventions or rest.^{8,19} Participants with an abandoned index AVF will continue with follow-up through 24-months and data will be collected on safety and interventions.

A HD AV access is not considered abandoned:

- If the participant discontinues use of the AV access due to kidney transplant, initiation of PD, or participant preference.
- During the maturation period or while waiting for a second stage procedure unless the principal investigator (PI) determines the participant requires and they then receive an alternative HD vascular access.

- During planned interventions, including transposition.
- If all reasonable efforts have not been attempted (and documented) to improve the condition of the access for it to be used.

A discontinuation of use of the clinical investigation AVF for any reason that does not meet this definition of access abandonment will be considered a temporary interruption.

Access Circuit Censoring Events include participant transfer to PD, kidney transplantation or the event of a participants premature discontinuation in the investigation due to withdrawn consent, withdrawal by PI, Lost to Follow-Up (LTF), or participant death (refer to Section 6.5 for definitions).

Adjunctive Procedure(s): Procedure(s) completed during the index procedure (prior to leaving the procedure room) as part of Standard-of-Care (SOC) procedures. These may include procedures to facilitate maturation and / or cannulation of the AVF, procedures to maintain use of the AVF, procedures to ensure HD continuity, as well as procedures to address AFs.

Second Stage Procedure(s): Facilitation Interventions (as defined below) intended to support the cannulation of arterialized vein segments that are determined to be needed a priori to or at the time of the index procedure (i.e. pre-planned facilitation interventions intended to support cannulation). Second stage procedures will not count against the intervention or patency endpoints and will require completion of the Second Stage Procedures eCRF.

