6.4 Participant Follow-Up

6.4.1 Follow-Up Intervals and Methods

All participants are to be followed according to the investigational site's SOC practices. In addition to the SOC visits, treated participants will have an investigation follow-up visit at 30-days and 6-weeks as well as 6- and 12-months post index procedure and will have a phone call follow-up at 3-, 18- and 24-months. For participants into whom the WavelinQTM EndoAVF System was introduced during the index procedure but procedure success was not achieved, only the follow up at 30-days will be completed and limited to the collection of safety events and interventions. This follow-up may be conducted by phone for these participants and investigation participation for these participants will end upon completion of this follow-up.

All follow-up must be performed by authorized delegated clinical investigation site team members. Follow-up windows will be calculated from the index procedure date. Refer to Section 1.3 for an overview of follow-up window time frames and requirements for each visit. The following data will be collected and documented on the appropriate eCRF for each follow-up unless otherwise specified for treated participants:

- DUS: A DUS assessment per the Ultrasound Guidelines must be performed at the follow-up visits at 30-days and 6-weeks for all treated participants and again at 6-and 12-months for participants not yet successfully dialyzing with the AVF created as part of this clinical investigation using 2-needle cannulation. The 6- and 12-month DUS are also required for participants that are using the AVF created as part of this clinical investigation but for whom procedure access was obtained at the wrist artery during the index procedure. The DUS for these participants will be limited to the examinations of the artery that was accessed during the index procedure. At minimum, images including the following characteristics are required and must be submitted to the Sponsor / Core Lab as per the details specified in the investigational site's regulatory binder:
 - o Arteries and veins of the AVF: Patency (including characterization of each stenosis, if present), and inner diameters. Brachial artery volume flow.
 - AV-anastomosis & juxta-anastomotic area: Patency (including characterization of each stenosis, if present).
 - o Cannulation veins: Patency (including characterization of each stenosis, if present) and inner diameters.

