 - o Perforator vein: Patency (including characterization of each stenosis, if present), as well as inner diameter and length.
 - Procedure access wrist artery (if used during index procedure): Patency (including characterization of each stenosis, if present), confirmation of flow, and inner diameter.

- Clinical Exam: Overall health and assessment of AV access function must be evaluated and documented with a physical exam conducted by the PI or authorized designee in accordance with each investigational site's SOC.
- *HD History and Status*: Determine and document if and how the participant has been and / or is receiving HD (AVF, CVC, etc.), and document the date of the participant's last HD session. Once HD (1- or 2-needle cannulation) is initiated via the AVF created as part of this investigation, HD details must be documented and detailed HD access data (e.g., cannulation logs) will be provided to the Sponsor or designee for review and analysis as follows:
 - Obetailed HD access data will be collected to indicate whether the participant successfully dialyzes with 2-needle AVF cannulation for at least 75% of HD sessions for three (3) continuous weeks and / or within 28 consecutive days. For the functional maturation and functional HD usability assessments, source documentation indicating HD success and vascular access used will be documented and collected until the endpoints are met (Sponsor verification is required before the clinical investigational site may stop collecting this HD access information).
 - O Thereafter determine and document if and how the participant has been and / or is receiving HD and whether the participant continues to be successfully dialyzed through the index AVF (the AVF created as part of the index procedure of this investigation) and document the date of the participant's last HD session.
- *SF-VAQ and EQ-5D Surveys:* Surveys will be completed by the participant or verbally read and documented by an authorized delegated investigation site team member for completion during the 6-week as well as 6-, 12- and 24-month followups.
- Documentation of AEs: Documentation of occurrence and / or status of AEs since the last follow up (refer to Section 8).
- Documentation of Interventions: Any access circuit interventions the participant has undergone since the index procedure and / or prior follow-up.

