#### 5.1.2 Primary Effectiveness Endpoint

The primary effectiveness endpoint of the clinical investigation is an effectiveness measure based on the number of interventions post creation to facilitate AVF use and / or maintain AVF use through the timepoint of the 6-month follow-up of the last active treated participant.

The primary effectiveness endpoint will be evaluated by the following hypothesis:

- H0: The number of interventions post creation to facilitate AVF use and / or maintain AVF use (Facilitation and / or Maintenance Interventions) per patient year (PY) of participants treated with the WavelinQTM EndoAVF System (RWE) is greater than or equal to that of the PG of 5 post creation facilitation and maintenance interventions / PY.
- H1: The number of interventions post creation to facilitate AVF use and / or maintain AVF use (Facilitation and / or Maintenance Interventions) per PY of participants treated with the WavelinQTM EndoAVF System (RWE) is less than that of the PG of 5 post creation facilitation and maintenance interventions / PY.

That is:

 $H_0$ : RWE  $\geq$  5 post creation facilitation and maintenance interventions / PY

H1: RWE < 5 post creation facilitation and maintenance interventions / PY

Rejection of the null hypothesis will signify that the number of interventions post creation to facilitate AVF use and / or maintain AVF use (Facilitation and / or Maintenance Interventions) per PY of AVFs created using the WavelinQTM EndoAVF System is less than the PG of 5 post creation facilitation and maintenance interventions / PY.

Facilitation and/ or maintenance intervention will be identified if:

On the Post-Procedure Intervention page, Date of Post Procedure Intervention is not NULL and before or on the cutoff date of the database lock, and Type of Intervention is checked as Facilitation and/ or Maintenance. Note in the event that there are multiple treatments performed during the same procedure driven by multiple reasons, each reason driving the intervention will be counted as a separate intervention.

For each participant, the number of interventions post creation to facilitate AVF use and / or maintain AVF use through the timepoint of the 6-month follow-up of the last active treated participant is expressed as:

(Number of observed facilitation and/or maintenance interventions \* 365) / Length of investigation duration (Days)

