Length of investigation duration (Days) is from the date of index procedure to the cutoff date of database lock (cutoff date – date of index procedure +1). If a participant discontinued early, then the last date of available study data (including the unscheduled visit date) will be used to calculate the length of investigation duration (last date of

available study data – date of index procedure +1). If a participant's endoAVF has permanent abandonment the date of permanent abandonment will be used to calculate the length of investigation duration (permanent abandonment date – date of index procedure +1).

The primary effectiveness analysis will be conducted on the AT population after the last active treated participant completes their 6-month follow-up; by this time, all participants still in the clinical investigation will have at least 6-months of data. The number of Facilitation and / or Maintenance Interventions per PY will be estimated by Poisson regression model with only the intercept term, and the estimate and 95% CI will be provided using the Wald method, and the p-value comparing to the PG will be calculated by a Chi-square test. The analysis will be repeated on the PP population.

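### The primary intervention rate credits person-time to the database-lock cutoff without a stated check that intervention status is known to that date

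*SAP*

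**What the plan says.** **Denominator (SAP 5.1.2).** The default rule is: "Length of investigation duration (Days) is from the date of index procedure to the cutoff date of database lock". There are two exceptions. Early discontinuers stop at their last available study data. For a permanently abandoned access, "the date of permanent abandonment will be used to calculate the length of investigation duration".

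**Numerator (SAP 5.1.2).** An intervention of the right type counts if its "Date of Post Procedure Intervention is not NULL and before or on the cutoff date of the database lock".

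**Timepoint.** Protocol 4.1.2 evaluates "all data collected for all participants up until the timepoint of the 6-month follow-up of the last active treated participant". SAP 2.7.1.2 and the formula wording in SAP 5.1.2 repeat that timepoint. No sentence says that the lock cutoff is that date.

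**When interventions are ascertained.** Protocol 6.4.1 collects at each follow-up "Any access circuit interventions the participant has undergone since the index procedure and / or prior follow-up". Clinic visits fall at 30 days, 6 weeks, 6 months and 12 months, and participants "will have a phone call follow-up at 3-, 18- and 24-months". After month 6 the scheduled checks are therefore at months 12, 18 and 24, counted from each participant's own index date.

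**After abandonment.** Protocol 4.4: "Participants with an abandoned index AVF will continue with follow-up through 24-months and data will be collected on safety and interventions". Abandonment is thus separate from the attrition assumed in Protocol 7.3.

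**The concern.** The cutoff is one calendar date, while scheduled checks follow each participant's own clock. A participant last seen at month 6 who is 11 months past the index procedure at the cutoff adds 5 months of denominator. Interventions in those months count only if something other than a scheduled contact has recorded them by lock.

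The direction is fixed. An unrecorded intervention lowers the numerator and leaves the denominator alone. An unrecorded abandonment lets person-time run on. Both push the rate down, towards success against the 5/PY goal, in a single-arm trial with no control group in which the same loss would cancel. For discontinuers the SAP ends person-time where data end; for active participants between visits it does not.

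**Working it through.** **1. The plan's own figure.** Inputs from Protocol 7.3: goal 5/PY, assumed rate 3.0/PY, more than 100 PY, two-sided 0.05. Success requires ln(x/PY) + 1.96/√x < ln 5, where x is the event count. At 100 PY this means x ≤ 456 (4.56/PY). The chance of success at a true 5/PY is 2.46%, and power at 3.0/PY exceeds 99.99%. The stated power of over 99% is reproduced.

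**2. Person-time at the cutoff.** Inputs:
- Enrollment of about 18 months (Protocol 3), taken as uniform, so time from index to cutoff T is uniform on 6 to 24 months.
- Attrition of 20%, 40% and 60% at 6, 12 and 24 months (Protocol 7.3). Retention S(t) is linear through 1, 0.8, 0.6 and 0.4.
- Visits on their target dates.

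With abandonment ignored:
- PY = 150 × E[∫S from 0 to T]/12. The integral over T is 45.6 (T from 6 to 12) + 153.6 (12 to 24) = 199.2. Then 199.2/18 = 11.07 months, and 150 × 11.07/12 = **138.3 PY**, consistent with the plan's more than 100.
- At risk at the cutoff = 150 × (6×0.70 + 6×0.55 + 6×0.45)/18 = **85**.
- Gap PY = 150 × E[S(T)(T − last visit)]/12, with last visit 6, 12 or 18. The three bands give 12.0 + 9.6 + 7.8 = 29.4. Then 29.4/18 = 1.633 months, and 150 × 1.633/12 = **20.4 PY**, which is 14.8% of 138.3.

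**3. Adding the abandonment stop.** Protocol 2.1.2 reports 77.3% cumulative patency ("Primary patency and cumulative patency were determined using the KM point estimates at month 6"). I assume this applies here and is independent of attrition, and multiply S(t) by an abandonment-free curve A(t):
- (i) constant hazard, A = exp(−ht) with h = −ln(0.773)/6 per month;
- (ii) linear to 0.773 at month 6, then flat.

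| | (i) | (ii) | Abandonment ignored |
|---|---|---|---|
| Total PY | 104.0 | 114.9 | 138.3 |
| At risk at cutoff | 48 | 66 | 85 |
| Gap PY | 10.9 | 15.8 | 20.4 |
| Gap share, no lag | 10.5% | 13.7% | 14.8% |
| Share, lock 1 month after cutoff | 7.7% | 9.8% | 10.5% |
| Share, 2 months | 5.2% | 6.4% | 6.9% |
| Share, 3 months | 3.1% | 3.7% | 4.0% |

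The lag rows hold the cutoff fixed and assume that visits falling due before lock are completed and entered, so that their look-back closes the gap.

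**4. Effect on the decision.** The documents give no capture rate, so the unrecorded share m of gap interventions is a range. Expected count = rate × PY × (1 − m × gap share), with a constant rate and exact Poisson probabilities.

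Example, case (i), true 5.0/PY, m = 25%: 5 × 103.99 × (1 − 0.25 × 0.1053) = 506.3 expected events. The success limit is 475, because ln(475/103.99) + 1.96/√475 = 1.6090 < ln 5 = 1.6094. P(X ≤ 475) = 8.5%.

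False success at a true 5.0/PY, cases (i)–(ii), nominal 2.5%:

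| Unrecorded in gap | No lag | 2-month lag | 3-month lag |
|---|---|---|---|
| 10% | 4.2–4.9% | 3.2–3.4% | 2.9% |
| 25% | 8.5–12.4% | 4.7–5.5% | 3.6–3.9% |
| 50% | 22–38% | 8.4–11.4% | 5.2–6.2% |

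With abandonment ignored, the no-lag column is 5.7%, 16.0% and 50.1%.

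Other true rates, no lag:
- 5.25/PY: 0.2–0.3%, 0.7–1.1% and 3–7% for 10%, 25% and 50% unrecorded.
- 5.5/PY: at most 0.5% (0.7% with abandonment ignored), even at 50%.
- 3.0/PY, 25% unrecorded: reported rate 2.90–2.92, and the goal is met in over 99% of trials.
- Falling rate (6.5–6.8/PY before month 6, 3/PY after, 5.0 overall): 3.4–3.7%, 5.3–6.9% and 10.5–16.1%.

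**The case against.** The strongest reply is that the rule is not biased in itself. Numerator and denominator share one cutoff, so complete recording gives an unbiased rate, and under a constant rate a later cutoff alone adds no bias. That stands.

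Capture also does not depend on scheduled contacts alone. Protocol 4.4 requires an Intervention eCRF for every intervention, not only for those found at a scheduled visit. Unscheduled visits (6.4.2), outside records (6.4.1), prompt adverse event recording (8.4) and monitoring with source verification (11.2.2) add further routes. Because the numerator goes by intervention date, events entered between cutoff and lock still count. A reader might infer that the gap is unobserved time and that the rate will be biased low. The documents do not support that: they show only that a scheduled check is missing there. Still, most of these routes are triggered by an event or a visit. None is stated to establish that an active participant with no entry had no intervention up to the cutoff.

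A reader might also infer that the SAP ignores the protocol's timepoint. It does not. SAP 2.5, 2.7.1.2 and 5.1.2 repeat it, and Protocol 7.7.3 presumes a single data cut. What is missing is one sentence equating the lock cutoff with that timepoint.

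Finally, the Data Management Plan (Protocol 10.3) and the derived data specification (SAP Appendix 2) were not available and may contain a pre-lock check. The point is therefore limited to the text that was reviewed.

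**Conclusion.** The point holds as a gap in the denominator rule that is cheap to close. About 10–14% of person-time (15% with abandonment ignored) falls after the last scheduled check if nothing is entered after the cutoff, and about 3–6% with a lock lag of two to three months. Missed visits would lengthen the gap, since one missed visit does not make a participant lost to follow-up (Protocol 6.5).

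Any under-recording makes the reported rate too low. It can change pass or fail only when the true rate is very close to 5/PY. It would be tempting to quote the 22–38% figure as the trial's error rate. That figure needs a true rate of exactly 5.0/PY, half of the gap interventions unrecorded and no entry after the cutoff, and the documents establish none of these. At the planned 3.0/PY the conclusion does not change.

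The missing 24-month stop has no effect if enrollment takes 18 months and the cutoff is the protocol timepoint. It matters if either runs longer.

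The sizes rest on uniform accrual, the protocol's attrition, on-time visits, premarket patency and an assumed capture range.

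**What to change.** In SAP 5.1.2:
- Define the cutoff as the 6-month follow-up of the last active treated participant, as in Protocol 4.1.2.
- Stop person-time at 24-month completion. Keep the discontinuation and abandonment stops.
- Before lock, confirm intervention and abandonment status through the cutoff for every active participant with a non-abandoned access, from existing contacts or HD-center records. The Protocol synopsis already provides for remote record collection.
- Keep all recorded data to the cutoff in the primary analysis, as Protocol 4.1.2 requires.
- Add a sensitivity analysis that ends both person-time and event counting at each active participant's last scheduled contact at which status was ascertained.
- Apply the same rules to the facilitation and maintenance rates in SAP 5.3.6, which reuse this definition.

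Cost: SAP wording and one status check for roughly 48–85 participants, with no new visit. The primary analysis loses no person-time up to the protocol timepoint. The sensitivity analysis uses about 93–118 PY (104.0 − 10.9 to 138.3 − 20.4), so it can fall below the stated 100 PY, though power at 3.0/PY stays above 99%. It overstates a falling rate: in the scenario above it reports 5.24–5.32/PY for a true 5.0. That is why it should not be the primary analysis.

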7.3 Sample Size Considerations

The sample size for the study of one-hundred and fifty (150) treated participants was established to assure adequate power for the primary safety and effectiveness endpoints as

well as to result in a sufficient sample size (when accounting for attrition) for assessment of the secondary and exploratory endpoints, specifically for those that only apply to subsets of the overall population (i.e. the incident population and wrist arterial procedure access population).

- 1) *Primary Safety Endpoint* The proportion of participants with freedom from device-or procedure-related SAEs through 30 days (ITT Population).
 - Assumptions:
 - The freedom from device- or procedure-related SAE rate for AVFs created using the WavelinQTM EndoAVF System is estimated at 92.6% through 30 days based on pre-market data;
 - The PG is set at 82.6% using a 10% non-inferiority margin;
 - The rate of attrition through 30 days is assumed to be 10%; and
 - o The Type 1 error is 0.05 (two-sided).
 - Sample Size:
 - A sample size of 150 treated participants [135 evaluable] will give over 92.5% power with a two-sided type I error of 0.05 as calculated using PASS 2019 (One Proportion Exact Test).
- 2) Primary Effectiveness Endpoint Interventions Post Creation to Facilitate AVF Use and / or Maintain AVF Use (Facilitation and / or Maintenance Interventions) through the Timepoint of the 6-Month Follow-Up of the Last Active Treated Participant (AT Population)
 - Assumptions:
 - The number of interventions post creation to facilitate AVF use and / or maintain AVF use after AVF creation using the WavelinQTM EndoAVF System is estimated at 3.0 / PY, a conservative assumption based on pre-market data;
 - The PG is set at 5 / PY to align with the targets and recommendations of the 2019 update of the KDOQI Clinical Practice Guideline for Vascular Access of < 2 interventions to facilitate and < 3 interventions to maintain AVF use;
 - The rate of attrition through 6-, 12-, and 24-months, including lost to followup, death, and other clinical investigation premature withdrawals is assumed to be 20%, 40%, and 60%, respectively; and
 - o The Type 1 error is 0.05 (two-sided).
 - Sample Size:
 - O A sample size of 150 treated participants, yielding more than 100 PY by the time the last active treated participant completes their 6-month follow-up, will give over 99% power with a two-sided type I error of 0.05 as calculated using PASS 2019 (One-Sample Poisson Rate Test).

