7.7.3 Handling of Missing Data

Investigation endpoints may have missing data due to a participant's withdrawal of consent, the withdrawal of a participant by the PI, a participant loss to follow-up and the death of a participant. Data may also be missing from investigation endpoints due to deviations and / or missing data collection. It is important to minimize missing data by all means and to always record the reason for omission.

For the primary safety endpoint, a conservative approach will be used for the handling of missing data: If a participant has a specified event (device-related or procedure-related SAE), the participant will be included irrespective of if the participant prematurely discontinues prior to the 30 day timepoint; if a participant prematurely discontinues before 30 days without the occurrence of a specified event, the participant will be considered not evaluable and will not be included in the primary safety endpoint analysis.

For the primary effectiveness endpoint, the Poisson regression model will be used to analyze the data. In the Poisson regression model, missing data handling is a standard part of the analysis: If a treated participant prematurely discontinues prior to the data cut, that participant's study duration will be considered as the period of time between the index procedure and their premature discontinuation, and the corresponding number of facilitation and/or maintenance interventions in that specific duration will be used for analysis.

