    - O A sample size of 150 treated participants, yielding more than 100 PY by the time the last active treated participant completes their 6-month follow-up, will give over 99% power with a two-sided type I error of 0.05 as calculated using PASS 2019 (One-Sample Poisson Rate Test).

Hence, the sample size of 150 treated participants will provide approximately 92.5%\*99%= 91.5% power for the co-primary endpoints.

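### The co-primary intervention rate does not stop person-time at kidney transplant or transfer to peritoneal dialysis, which pulls it toward the 5/PY goal

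*SAP*

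**What the plan says.** SAP 5.1.2 runs each participant's person-time from the index procedure to the database-lock cutoff, with two exceptions. Early discontinuation moves the end to the last available study data. For a failed fistula, "If a participant's endoAVF has permanent abandonment the date of permanent abandonment will be used to calculate the length of investigation duration". Protocol 7.7.3 has only the first exception: on premature discontinuation before the data cut, "that participant's study duration will be considered as the period of time between the index procedure and their premature discontinuation".

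Transplant and PD transfer trigger neither exception.

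- Protocol 4.4 lists among the situations in which an access is not abandoned: "If the participant discontinues use of the AV access due to kidney transplant, initiation of PD, or participant preference".
- The same section treats them as a category beside leaving the study: "Access Circuit Censoring Events include participant transfer to PD, kidney transplantation or the event of a participants premature discontinuation in the investigation".
- Protocol 6.5 does not name either as a reason for discontinuation. Its list is open-ended, but nothing in it makes these events a discontinuation.

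Other SAP analyses do act on these events. Cannulation success (5.2.3), functional maturation (5.3.4), HD usability (5.3.5), primary and cumulative patency (5.3.7, 5.3.8), CVC removal (5.3.10.1) and the supportive safety Kaplan-Meier analysis (5.1.1) censor at PD start or transplant. Physiological maturation (5.2.2) and the two functional patency endpoints (5.2.4, 5.3.9) treat such participants as not evaluable if the event precedes the relevant window without the outcome.

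**The concern.** Protocol 4.5.1 presents the endpoint as the burden of getting and keeping a functional access, judged against guideline targets. After a transplant or a move to PD the fistula is largely not needed for haemodialysis, so few facilitation or maintenance procedures are expected. That time still enters the denominator. The bias has one direction, toward a lower rate and toward declaring the goal met, and it arises even if every intervention is recorded.

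The SAP already applies at-risk reasoning to this endpoint. In 5.3.6 item 3 it extends person-time past abandonment for the all-interventions rate because HD continuity procedures can still occur then, and it contrasts this with facilitation and maintenance. The co-primary clock thus stops at abandonment because the counted events are no longer expected. The same argument covers the protocol's own access censoring events.

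At stake is the false-success rate of a confirmatory test, nominally 2.5% in the success direction, when the at-risk rate is close to the goal.

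**Working it through.** **Inputs from the documents.** Goal: "The PG is set at 5 / PY to align with the targets and recommendations". Planning rate: "is estimated at 3.0 / PY, a conservative assumption based on pre-market data". Person-time: 150 treated participants, "yielding more than 100 PY by the time the last active treated participant completes their 6-month follow-up". Type I error 0.05 two-sided. Attrition 20/40/60% at 6/12/24 months (protocol 7.3, SAP 2.4). Enrolment about 18 months (protocol section 3).

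**Assumptions.** Uniform enrolment, linear attrition between the stated points, a constant annual hazard h of transplant or PD, and participants staying in the study after it. The documents give no value for h.

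**1. The plan's power figure.** With x events, the log-Wald upper limit is below 5 when (x/PY) × exp(1.96/√x) < 5. At 100 PY this needs x ≤ 456, since 4.56 × exp(1.96/√456) = 4.998. Power at 3.0/PY exceeds 99.9%, so the stated figure of over 99% reproduces.

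**2. Expected person-time.** Follow-up at the cutoff is uniform on 6 to 24 months. Mean retained time is 7.6 months for planned follow-up between 6 and 12 months, and 12.8 months for 12 to 24. The average is (6 × 7.6 + 12 × 12.8)/18 = 11.07 months. Person-time is 150 × 11.07/12 = 138.3 PY. The test then passes at x ≤ 640 (4.63/PY).

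**3. Share of person-time after the event.** With S(t) the retention curve, f is the integral of S(t)(1 − exp(−ht)) divided by the integral of S(t), both averaged over follow-up. This gives f = 2.9, 5.7 and 8.4% for h = 5, 10 and 15% per year.

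**4. Chance of passing when the at-risk rate is exactly 5.0/PY.** The counted rate is 5(1 − f) + r·f, where r is the rate after the event. The chance of passing is P(Poisson(138.3 × counted rate) ≤ 640).

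| h per year | f | At-risk PY | Counted rate, r = 0 | Chance of passing | Counted rate, r = 1 | Chance of passing |
|---|---|---|---|---|---|---|
| 0 | 0 | 138 | 5.000 | 2.5% | 5.000 | 2.5% |
| 5% | 2.9% | 134 | 4.855 | 11% | 4.884 | 9% |
| 10% | 5.7% | 130 | 4.715 | 32% | 4.772 | 22% |
| 15% | 8.4% | 127 | 4.580 | 61% | 4.664 | 43% |

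The pattern does not depend on the accrual model: at f = 5% and r = 0 the chance is 20% with 100 PY and 26% with 138 PY.

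**5. At the planning rate.** With 3.0/PY at risk and r = 0, the counted rate is 3 × (1 − 0.057) = 2.83 at h = 10%. The test passes under either rule.

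**6. With person-time stopped at the event.** At-risk person-time is 134, 130 or 127 PY, and the success limits are 620, 601 or 584 events. Error in the success direction is 2.3 to 2.5%, and power at 3.0/PY stays above 99.9%.

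**The case against.** The strongest reply is that the rule is a choice of estimand. Protocol 4.1.2 asks for all data on all participants up to the timepoint, 7.7.3 shortens duration only for premature discontinuation, and access censoring events are invoked in the patency definitions but not in 4.1.2. Interventions per patient-year in everyone treated is a coherent quantity. This stands in part: the protocol wording would have to change too. It does not settle the matter, because SAP 5.1.2 already departs from all-data counting by stopping at abandonment.

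Second, the fistula is not risk-free after these events. Maintenance interventions in protocol Table 1 include treatment of aneurysm and access infection, and protocol 4.4 classes such an interruption as temporary, so a return to use is possible. This stands. It is why a range for r is shown and why later interventions should still be reported.

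Third, participants who leave the study at transplant or PD are already cut at their last data, and some may sit within the assumed attrition. If so, f is smaller than shown.

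Fourth, the effect matters only near the goal. At an at-risk rate of 5.5/PY with r = 0, the chance of passing is about 0.01, 0.2 and 1.6% for the three hazards. At 4.0/PY or below the test passes either way. This also stands.

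A reader might infer that the co-primary rate is the only analysis without the rule. It is not. The binary primary safety endpoint, the secondary SAE proportions (SAP 5.2.1), all four rates in 5.3.6 and total CVC exposure (5.3.10.4) have none either. For the SAE proportions that is reasonable, since a related SAE can still occur.

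**Conclusion.** The point holds. Two of the access censoring events named in the protocol do not stop the clock for the co-primary intervention rate, and the resulting bias favours success. The omission and its direction come from the text. That the fistula is largely not at risk afterwards is an inference, supported by protocol 4.4.

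The size is conditional on assumed hazards of 5 to 15% per year, participants remaining in follow-up, and an at-risk rate of exactly 5.0/PY. Under those conditions, false success rises from 2.5% to between 9% and 61% across the two values of r.

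A reader might also infer that the trial's expected conclusion is unsafe. The documents do not support that: nothing changes at 3.0/PY, and the stated power is not in dispute. What is not protected is the stated type I error for the at-risk rate near the goal.

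**What to change.** Before database lock:

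- In SAP 5.1.2 and 5.3.6 items 1 and 2, end both person-time and event counting at the earliest of the cutoff, last available study data, permanent abandonment, PD start and kidney transplant.
- Align protocol 4.1.2 and 7.7.3 with that rule, including the abandonment stop that the SAP already uses.
- Report the current full-follow-up rate, with any interventions after transplant or PD, as a sensitivity analysis.

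The PD and transplant dates are already used elsewhere in the SAP. The cost is a small protocol wording change, a slightly less favourable rate, and a few percent of person-time: about 138 to 130 PY at the 10% hazard, still above the planned 100. Settling this before results are seen avoids the appearance of a data-driven denominator.
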